5.4.2.1. Combined Solicited and Unsolicited Adverse Events

For clintrial.gov and EudraCT posting purposes, a summary of combined solicited and unsolicited non-serious adverse events will be produced by System Organ Class and preferred terms and according to occurrence of each event.

A summary of subjects with all combined solicited (regardless of their duration) and unsolicited adverse events will be provided. Solicited adverse events will be coded by MedDRA as per the following codes.

Solicited symptom	Lower level term code	Corresponding Lower level term decode
PA	10022086	Injection site pain
RE	10022098	Redness at injection site
SW	10053425	Swelling at injection site
TE	10016558	Temperature/Fever
FU	10022998	Irritability/Fussiness
DR	10013649	Drowsiness
LO	10003028	Loss of appetite
LS	10060708	Large injection swelling

6. ANALYSIS INTERPRETATION

All analyses are descriptive.

7. CONDUCT OF ANALYSES

Any deviation(s) or change(s) from the original statistical plan outlined in this protocol will be described and justified in the final study report.

7.1. Sequence of analyses

The final analyses of all data will be conducted when all data are available. This analysis will include the final analysis of immunogenicity and the final analysis of solicited and unsolicited symptoms and SAEs. A clinical study report containing all data will be written and made available to the investigators.

Description	Analysis ID	Disclosure Purpose (CTRS=public posting, SR=study report, internal, public posting)	Dry run review needed (Y/N)	Study Headline Summary (SHS) requiring expedited communication to upper management (Yes/No)	Reference for TFL
Final	E1_01	SR	Yes	Yes	TFL TOC

7.2. Statistical considerations for interim analyses

No interim analysis is planned for this study.

8. CHANGES FROM PLANNED ANALYSES

- During the course of the study, the assays used to measure the anti-D, anti-T, anti-PT, anti-FHA and anti-PRN IgG concentrations were re-developed and re-validated and both assay units and assay cut-offs were adapted. The new ELISA's for PT, FHA and PRN were calibrated against the WHO International Standard (NIBSC 06/140). This allowed the expression of concentrations measured with the new ELISA's in international units per milliliter (IU/mL) instead of the formerly used ELISA units per milliliter (ELU/mL). The newly validated DTPa ELISA's used in the study have a lower assay cut-off as compared to the one described in the protocol. The current assay cut-off is 0.057 IU/mL for anti-D, 0.043 IU/mL for anti-T, 2.693 IU/mL for anti-PT, 2.046 IU/mL for anti-FHA and 2.187 IU/mL for anti-PRN. An agreement between the old and new ELISAs was shown with regards to the two thresholds of clinical relevance for the DI/TE response (0.1 IU/mL and 1.0 IU/mL) and therefore the clinical endpoints and anti-D and anti-T are unchanged. In the absence of a correlate of protection for the B. pertussis antigens, the pertussis endpoints were redefined based on the assay cut-off (see section 5.7.5 of protocol).

CONFIDENTIAL

201334 [DTPA (BOOSTRIX) -049 BST: 048]
Statistical Analysis Plan Final

- Note: Due to re-validation of all assays, the cut-offs presented in Table 7 of the protocol of few antigens have changed. Below table has an updated threshold.

Antigen	Threshold for positivity
• Anti-PT	• 2.693 IU/mL
• Anti-FHA	• 2.046 IU/mL
• Anti-PRN	• 2.187 IU/mL
• Anti-D	• 0.057 IU/mL
• Anti-T	• 0.043 IU/mL
• Anti-polio	• 8 dilution
• Anti-PRP	• 0.066 µg/mL
• Anti-HBs	• 6.2 mIU/mL
• Anti-pneumococcal serotypes (1)	• 0.080 µg/mL
• Anti-pneumococcal serotypes (3)	• 0.075 µg/mL
• Anti-pneumococcal serotypes (4)	• 0.061 µg/mL
• Anti-pneumococcal serotypes (5)	• 0.198 µg/mL
• Anti-pneumococcal serotypes (6A)	• 0.111 µg/mL
• Anti-pneumococcal serotypes (6B)	• 0.102 µg/mL
• Anti-pneumococcal serotypes (7F)	• 0.063 µg/mL
• Anti-pneumococcal serotypes (9V)	• 0.066 µg/mL
• Anti-pneumococcal serotypes (14)	• 0.160 µg/mL
• Anti-pneumococcal serotypes (18C)	• 0.111 µg/mL
• Anti-pneumococcal serotypes (19A)	• 0.199 µg/mL
• Anti-pneumococcal serotypes (19F)	• 0.163 µg/mL
• Anti-pneumococcal serotypes (23F)	• 0.073 µg/mL

- Also refer to the additional considerations section specific to each analysis of demography, immunogenicity and safety for additional updates to the planned analyses.

9. NON-STANDARD DATA DERIVATION RULES AND STATISTICAL METHODS

The following sections describe additional derivation rules and statistical methods which are not presented in section 10.1 (Business rules for standard data derivations and statistical methods).

9.1. Data derivation

9.1.1. Congenital anomalies (CA)

Congenital anomalies (CA) are considered events of specific interest in maternal immunization programs and mostly recommended follow-up period seen in literature of infants born to mothers vaccinated during pregnancy is until 6 months of age. As per protocol, in Boostrix-047 study the follow-up period of infants after birth was two months. Hence, some CAs were not yet diagnosed and/or reported during the study Boostrix-047 and so these events have been reported in General Medical History section of infants in Boostrix-048 or in Boostrix-049 study. Given the importance of these safety data, medical coding of congenital anomalies reported in GMH section of Boostrix-048 (201330) and Boostrix-049 (201334) will be done. Since these CAs were not reported as SAEs and only the diagnosis code in verbatim was provided, the coding using the standard MedDRA query for the narrow CA will be performed.

An overview of all congenital anomalies both reported as unsolicited events and as pre-existing conditions in GMH section in these three studies will be present in Boostrix-049 study report, as this is the last study.

9.1.2. Ages & Stages Questionnaires (ASQ-3)

For the ASQ-3 analysis: The threshold value (cut off corresponding to the black zone) for each of the domain at time point month 9 and 18 are as follows [Squires, J., & Bricker, D., 2009].

Domain	Cut off (Month 9)	Cut off (Month 18)
Communication	13.97	13.06
Gross Motor	17.82	37.38
Fine motor	31.32	34.32
Problem Solving	28.72	25.74
Personal –Social	18.91	27.19

9.2. Statistical Method

If all subjects with ASQ-3 score in the black zone for at least one domain have BSID-III results, the clopper and Pearson CI will be used for the % of subjects with neurodevelopmental impairment.

If some subjects with ASQ-3 score in the black zone for at least one domain have no BSID-III results, the Greenwood formula [S.Sawyer,2003] for censored BSID-III data

will be used to estimate the % of subjects with neurodevelopmental impairment and associated CI.

10. ANNEXES

10.1. Business rules for standard data derivations and statistical methods

This section contains GSK Vaccines' standard rules for data display and derivation for clinical and epidemiological studies. These rules will be applied along with those detailed in section 9 (additional study-specific rules).

10.1.1. Attributing events to vaccine doses

NA.

10.1.2. Handling of missing data

10.1.2.1. Dates

When partially completed dates (i.e. with missing day or month) are used in calculations, the following standard rules will be applied:

- A missing day will be replaced by 15
- A missing day and month will be replaced by June 30th.

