3.4. Secondary endpoints

- Immunogenicity with respect to components of *Infanrix hexa* and *Prevenar 13*.

Before the booster dose

- Anti-diphtheria, anti-tetanus, anti-poliovirus type 1, anti-poliovirus type 2, anti-poliovirus type 3, anti-HBs and anti-PRP seroprotection status.
- Anti-PT, anti-FHA and anti-PRN and anti-pneumococcal serotypes (1, 3, 4, 5, 6A, 6B, 7F, 9V, 14, 18C, 19A, 19F, 23F) seropositivity rates.
- Anti-diphtheria, anti-tetanus, anti-PT, anti-FHA, anti-PRN, anti-poliovirus type 1, anti-poliovirus type 2, anti-poliovirus type 3, anti-HBs and anti-pneumococcal serotypes (1, 3, 4, 5, 6A, 6B, 7F, 9V, 14, 18C, 19A, 19F, 23F) and anti-PRP antibody concentrations or titres.

One month after the booster dose

- Anti-diphtheria, anti-tetanus, anti-poliovirus type 1, anti-poliovirus type 2, anti-poliovirus type 3, anti-HBs, anti-PRP, anti-PT, anti-FHA, anti-PRN and anti-pneumococcal serotypes (1, 3, 4, 5, 6A, 6B, 7F, 9V, 14, 18C, 19A, 19F, 23F) antibody concentrations or titres.
- Anti-PT, anti-FHA, anti-PRN antibody seropositivity rates.
- Solicited local and general symptoms.
 - Occurrence of solicited local/general symptoms during the 4-day (Day 0-Day 3) follow-up period after booster vaccination.
- Unsolicited adverse events.
 - Occurrence of unsolicited symptoms during the 31-day (Day 0-Day 30) follow-up period after booster vaccination.
- Serious adverse events.
 - Occurrence of reported SAEs from booster dose up to study end.
- Neurodevelopmental status will be assessed at 9 and 18 months of age adjusted for prematurity.
 - Proportion of infants with an ASQ-3 score in the black zone in any domain.
 - Proportion of infants with an ASQ-3 score in the black zone for gross motor skills.
 - Proportion of infants with an ASQ-3 score in the black zone for fine motor skills.
 - Proportion of infants with an ASQ-3 score in the black zone for communication.
 - Proportion of infants with an ASQ-3 score in the black zone for problem solving skills.
 - Proportion of infants with an ASQ-3 score in the black zone for personal-social skills.
 - Proportion of infants referred for formal neurodevelopmental evaluation using BSID-III.

- Proportion of infants with at least one of the indicators of neurodevelopmental impairment using BSID-III.

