- The verbatim reports of unsolicited AEs will be reviewed by a physician and the signs and symptoms will be coded according to MedDRA. Every verbatim term will be matched with the appropriate Preferred Term. The percentage of subjects with unsolicited AEs occurring within 31-day (Day 0- Day 30) follow-up period after any dose with its exact 95% CI [Clopper, 1934] will be tabulated by group, and by preferred term. Similar tabulation will be done for unsolicited AEs rated as grade 3, for unsolicited AEs with causal relationship to vaccination and AEs/SAEs leading to withdrawal from the study.
- The percentage of subjects who receive concomitant medication and antipyretic medication during the 4-day (Day 0- Day 3) follow-up period and during the entire study period will be tabulated (with exact 95% CI [Clopper, 1934]) after the booster dose.
- Any large injection site reaction (defined as any local swelling with diameter > 50 mm and/or any noticeable diffuse injection site swelling (diameter not measurable) and/or any noticeable increased circumference of the injected limb) reported within 4 days (Day 0-Day 3) following the booster dose will be described in detail.
- Subjects who experience at least one SAE from booster vaccination up to study end will be described in detail.
- Subjects who report at least one SAE after the end of primary study 201330 [DTPA (BOOSTRIX)-048 PRI] and before 201334 [DTPA (BOOSTRIX)-049 BST: 048] study will be described in detail.
- Withdrawal due to AEs and SAEs following vaccinations will be described in detail.
- For the subjects who withdraw from the study after Visit 1 (after completion of ASQ-3 questionnaire but have not received booster vaccination), the analysis will be performed on the Total enrolled cohort.
- Neurodevelopmental status of the subjects will be assessed depending on the ASQ-3 score. The proportion of subjects in the black zone for any domain, for gross motor skills, fine motor skills, communication, problem solving skills and personal-social skills will be tabulated. The proportion of infants referred for formal neurodevelopmental evaluation using BSID-III and those with at least one indicators of neurodevelopmental impairment using BSID-III will also be tabulated.

Handling of missing data:

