5.4.2. Additional considerations

- The AEs/SAEs leading to withdrawal from the study will be generated as a listing instead of a table.
- The verbatim reports of unsolicited AEs will be reviewed by a physician and the signs and symptoms will be coded according to MedDRA. Every verbatim term will be matched with the appropriate Preferred Term. The percentage of subjects with unsolicited AEs occurring within 31-day (Day 0- Day 30) follow-up period after the booster dose with its exact 95% CI [Clopper, 1934] will be tabulated by group, and by preferred term.
- Subjects who report at least one SAE after the end of primary study 201330 [DTPA (BOOSTRIX)-048 PRI] and before the booster vaccination in 201334 [DTPA (BOOSTRIX)-049 BST: 048] study will be described in detail.
- The percentage of subjects with congenital anomaly reported across the three studies (047, 048 and 049) with its exact 95% CI [Clopper, 1934] will be tabulated by group, and by preferred term. The details of this analysis are detailed in section 9.
- The neurodevelopmental status of infants will be tabulated at both month 9 and 18.

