10.1.3.8. Onset day

The onset day for an event (e.g. AE, medication, vaccination) is the number of days between the last study vaccination and the start date of the event. This is 1 for an event occurring on the same day as a vaccination (and reported as starting after vaccination).

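### The partial-date rule in SAP 10.1.2.1 has no limit at the booster date or at Day 30, so unsolicited adverse events with a missing start day can be dated out of the 31-day window

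*SAP*

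**What the plan says.** SAP 10.1.2.1 sets the scope: "When partially completed dates (i.e. with missing day or month) are used in calculations, the following standard rules will be applied". Two rules follow: "A missing day will be replaced by 15" and "A missing day and month will be replaced by June 30th". Neither carries a condition.

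The dates feed two safety outputs.

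- **Unsolicited events.** SAP 5.4.1 and 5.4.2 tabulate "unsolicited AEs occurring within 31-day (Day 0- Day 30) follow-up period after the booster dose". SAP 10.1.3.8 derives the onset day, which "is the number of days between the last study vaccination and the start date of the event".
- **Serious events.** The secondary endpoint in SAP 3.4 is "Occurrence of reported SAEs from booster dose up to study end". SAP 5.4.2 separately describes "Subjects who report at least one SAE after the end of primary study 201330" and before the booster, so the booster date divides the two summaries.

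Nothing else in the documents bounds an imputed start date. SAP 10.1.1, on attributing events to doses, is marked not applicable. SAP 10.1.2.4 deals only with missing severity, relationship and outcome. SAP section 9 adds rules for congenital anomalies, the ASQ-3 and the BSID-III. The missing-data text in protocol section 10.5 does not mention partial dates.

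**The concern.** Protocol 8.2.1 collects adverse events with onset from Day 0 to Day 30 after the booster, and protocol 8.1.1 sends conditions present before vaccination to the medical history. A non-serious event on the adverse-event form is therefore already known to belong in the window, with rare exceptions. The imputation rule ignores that knowledge and can give such an event a date that contradicts the form on which it was recorded.

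Two examples show both edges:

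- Booster on 20 May, event in May with the day missing: dated 15 May, which is Day -5.
- Booster on 10 May, event in June with the day missing: dated 15 June, which is Day 36. The window itself closes on 9 June.

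Applied as written, both events drop out of a secondary safety table. For true Day 0-30 events the error runs only one way, because the rule can remove them but cannot add any.

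**Working it through.** The documents give no figure for this, so there is none to reproduce.

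**Assumptions (not in the documents).** Booster dates evenly spread over every day from 1 January 2016 to 31 December 2019 (1,461 dates); true onset uniform over offsets 0 to 30; month known, day missing and set to the 15th. That makes 1,461 x 31 = 45,291 combinations of booster date and onset.

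**Dated before the booster.** This happens when the booster falls on day v of the month with v at least 16 and onset is in the same month. In a month of length L there are L - v + 1 such onsets, and summing over v from 16 to L gives (L - 15)(L - 14)/2.

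- 31-day month: 16 x 17/2 = 136; 30-day month: 15 x 16/2 = 120; February: 13 x 14/2 = 91, or 14 x 15/2 = 105 in a leap year.
- Four years: 4 x (7 x 136 + 4 x 120) + 3 x 91 + 105 = 6,106.
- 6,106/45,291 = 13.5%.

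**Dated after Day 30.** For onset in the following month the imputed offset is L - v + 15, which exceeds 30 when v is at most L - 16. Each such booster date has 30 - L + v onsets in that month.

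- 31-day month: 0 + 1 + ... + 14 = 105; 30-day month: 1 + ... + 14 = 105; February: 102, or 104 in a leap year.
- Late-January boosters whose window reaches March add 3, or 1 in a leap year.
- Every year totals 11 x 105 + 105 = 1,260; four years give 5,040.
- 5,040/45,291 = 11.1%.

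**Total.** (6,106 + 5,040)/45,291 = 24.6%.

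**Only the year known.** Taking booster dates in 2018, an in-window event stays in only if 30 June lies within 30 days after the booster, which means boosters from 31 May to 30 June. That is 31 of 365 dates, so 1 - 31/365 = 91.5% fall outside.

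**Sensitivity, day missing:**

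| Assumption | Before booster | After Day 30 | Outside |
|---|---|---|---|
| Uniform onset | 13.5% | 11.1% | 24.6% |
| Exponential onset, scale 15 days | 23.0% | 4.7% | 27.8% |
| Exponential onset, scale 10 days | 27.4% | 2.8% | 30.2% |
| Exponential onset, scale 7 days | 32.1% | 1.4% | 33.4% |
| Exponential onset, scale 3 days | 42.5% | 0.0% | 42.5% |
| Onset on Days 0-3 only | 45.8% | 0.0% | 45.8% |

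Restricting boosters to weekdays leaves the uniform result at about 24.6%. A one-day shift in how the window is coded gives 26.2% to 26.4%. That shift is possible because SAP 10.1.3.8 numbers a same-day event as 1 while the window starts at Day 0.

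**Effect of limits.** A floor at the booster date alone takes the uniform total from 24.6% to 11.1%. Adding a cap at Day 30 takes it to 0% for true in-window events.

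**Serious events with a missing day.** Of those beginning in the 31 days from the booster, 13.5% are dated before it. Of those beginning in the 31 days before it, 11.1% are dated on or after it. An automatic floor would send every same-month event to the post-booster side. For a booster on day v, that is v - 1 of the 31 preceding days, giving 21,520/45,291 = 47.5% in place of 11.1%.

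**The case against.** The strongest reply is that partial dates will be rare. Diary cards are handed out at the vaccination visit and checked with the parents at Visit 3 (protocol 5.6.2.14), omissions in the case report form are queried (11.1), and source data are verified (11.2). Serious events are reported within 24 hours and updated (8.3.3). The rule is also a company-standard midpoint convention, nothing in it acts differently by group, and every analysis is descriptive. All of this stands. It means the effect on the reported percentages cannot be sized and may be negligible, but it does not make the rule correct for the dates to which it is applied.

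A reader might infer more than the documents support:

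- **That a quarter of adverse events are lost.** The 24.6% applies only to events whose start day is missing.
- **That the missing floor at vaccination is the whole cause.** It accounts for 13.5 of the 24.6 points; the other 11.1 come from the missing cap at Day 30.
- **That nearly half of early reactions vanish.** The 45.8% concerns unsolicited events on Days 0-3 with a missing day. Solicited symptoms are recorded daily and have their own rules in SAP 10.1.2.3.2.
- **That serious events disappear.** Those before and after the booster are both to be described in detail (SAP 5.4.1 and 5.4.2). A crossing event is relabelled, and crossing runs in both directions.

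**Conclusion.** The concern holds as a minor fault in a stated rule. For a non-serious unsolicited event that truly began on Day 0-30 and has a missing start day, the chance of being dated outside the window is 24.6% with evenly spread booster dates and uniform onset. It is higher, 27.8% to 42.5% in the exponential cases above, if onset is concentrated soon after vaccination. With only the year known it is 91.5%. These are conditional rates with no known denominator, and the denominator is probably small. No test is affected, and the documents give no reason to expect a difference between groups. For serious events the consequence is a possible wrong label relative to the booster, not an omission.

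**What to change.** Add to SAP 10.1.2.1, for start dates only:

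- **Non-serious unsolicited events.** If the known month overlaps Day 0-30 (or the known year does, when the month is missing), take the standard imputed date, then limit it to no earlier than the booster date, no later than Day 30 and no later than the recorded end date. Query any event whose end date precedes the booster. The downside is that an occasional event from outside the window may be counted in, which should be rare because collection of these events is confined to that window.
- **Serious events.** Assign a partial date to the pre- or post-booster period from what the record shows about onset relative to vaccination. Apply the booster-date floor only when the record shows onset after vaccination, because an automatic floor would mislabel pre-booster events far more often than the present rule does (47.5% against 11.1%). The summary from booster to study end needs no Day 30 cap.

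When programming the window, reconcile the same-day value of 1 in SAP 10.1.3.8 with the Day 0 start. The cost is a few sentences in the SAP and a small change to the date derivation, with no new data collection.

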10.1.2.2. Laboratory data

Missing laboratory results (including immunological data) will not be replaced.

10.1.2.3. Daily recording of solicited symptoms

10.1.2.3.1. Studies with electronic diaries

NA.

10.1.2.3.2. Studies with paper diaries

For studies using paper diaries which have questions in the CRF indicating the presence or absence of solicited symptoms, the following rules are applicable.

Denominators for the summary of local (or general) solicited symptoms will be calculated using the number of subjects who respond "Yes" or "No" to the question concerning the occurrence of local (or general) symptoms.

When a specific symptom is marked as having not occurred following a specific vaccination for the specified post-vaccination period for the symptom in question, all daily measurements will be imputed as Grade 0.

When a specific symptom is marked as having occurred following a specific vaccination for the specified post-vaccination period for the symptom in question, any missing daily recordings will be given imputed values to allow them to contribute to the ‘Any’ rows but not to specific grade rows of the symptom summary tables.

When the occurrence of a specific symptom is not present (for the specified post-vaccination period for the symptom in question) but the group of symptoms (local or general) is marked as having occurred, all missing daily recordings will be given imputed values to allow them to contribute to the ‘Any’ rows but not to specific grade rows of the symptom summary tables.

The following table shows how subjects contribute to each category for a specific solicited symptom over the Day 0 to Day 3 post-vaccination period:

Solicited symptom category	Subjects included in the calculation of the numerator
Any	All subjects with at least one occurrence of the symptom at grade 1, grade 2, or grade 3 between Day 0 and Day 3 or with the symptom marked as present and at least one missing daily recording between Day 0 and Day 3
At least grade 1	All subjects with at least one occurrence of the symptom at grade 1, grade 2, or grade 3 between Day 0 and Day 3
At least grade 2	All subjects with at least one occurrence of the symptom at grade 2 or grade 3 between Day 0 and Day 3
At least grade 3	All subjects with at least one occurrence of the symptom at grade 3 between Day 0 and Day 3

For a given subject and the analysis of solicited adverse events within 4 days post-vaccination, missing or non-evaluable measurements will not be replaced. Therefore, the analysis of the solicited adverse events based on the Total Vaccinated Cohort will include only vaccinated subjects for doses with documented safety data (i.e., symptom screen completed). More specifically the following rules will be used:

- Subjects who documented the absence of a solicited adverse events after one dose will be considered not having that adverse events after that dose.
- Subjects who documented the presence of a solicited symptom and fully or partially recorded daily measurement over the solicited period will be included in the summaries at that dose and classified according to their maximum observed daily recording over the solicited period.
- Subjects who documented the presence of a solicited symptom after one dose without having recorded any daily measurement will be assigned to the lowest intensity category at that dose (i.e., 37.5°C for fever or grade 1 for other symptoms).
- Doses without symptom sheets documented will be excluded.

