#### **5.6.2.14. Recording of AEs and SAEs**

- Refer to Section 8.2 for procedures for the investigator to record AEs and SAEs. Refer to Section 8.3 for guidelines and how to report SAE reports to GSK Biologicals.
- The subjects' parent(s)/LAR(s) will be instructed to contact the investigator immediately should the subjects manifest any signs or symptoms they perceive as serious.
- Record large injection site reactions as described in 8.1.3.1.
- At the vaccination visit (Visit 2), diary cards will be provided to the subject's parent(s)/LAR(s). The subject's parent(s)/LAR(s) will record body (axillary/rectal) temperature and any solicited local/general AEs (i.e., on the day of vaccination and during the next three days) or any unsolicited AEs (i.e., on the day of vaccination and during the next 30 days) occurring after vaccination. The subject's parent(s)/LAR(s) will be instructed to return the completed diary card to the investigator at the next study visit.
- Collect and verify completed diary cards during discussion with the subject's parent(s)/LAR(s) at Visit 3.
- Any unreturned diary cards will be sought from the subject's parent(s)/LAR(s) through telephone call(s) or any other convenient procedure. The investigator/*designee* will transcribe the collected information into the eCRF in English. **(Amended 12 December 2016)**

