**Table 12 Solicited general adverse events**

Drowsiness
Fever
Irritability/Fussiness
Loss of appetite

Note: Temperature will be recorded in the evening. Should additional temperature measurements be performed at other times of day, the highest temperature will be recorded in the eCRF.

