10.1.3.5. Temperature

- Temperatures will be presented in degrees Celsius (°C). Temperatures reported in degrees Fahrenheit (°F) will be converted as follows:

$$\text{Temperature (Celsius)} = ((\text{Temperature (Fahrenheit)} - 32) \times 5) / 9$$

The result is rounded to 1 decimal.

- The intensity of fever measured by oral, axillary or tympanic route will be scored as defined in the protocol. If in case, measured by rectal route, then the scoring will be performed as below to integrate the results with the other routes.

0	<38°C
1	≥38.0°C to ≤39.0°C
2	>39.0°C to ≤40.0°C
3	>40.0°C

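### Read literally, the SAP's Grade 0 rule for a symptom marked as not occurred also overwrites recorded temperatures and diameters, and no passage says which entry prevails

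*SAP*

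**What the plan says.** SAP 10.1.2.3.2 handles solicited symptoms from paper diaries according to how the yes/no question was answered.

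- Marked as not occurred: "all daily measurements will be imputed as Grade 0".
- Marked as occurred: "any missing daily recordings will be given imputed values to allow them to contribute to the" Any rows of the summary tables. A third rule, for a symptom left unanswered when its group is marked as present, is likewise limited to missing recordings.
- A later list in the same section states: "Subjects who documented the absence of a solicited adverse events after one dose will be considered not having that adverse events after that dose". The next item, "Subjects who documented the presence of a solicited symptom and fully or partially recorded daily measurement over the solicited period will be included", is the one that classes an infant by the highest reading observed, and it applies only where presence was documented.

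Elsewhere the measured symptoms are driven by the value. Protocol Table 14 has the parent record a temperature for fever and the greatest diameter in mm for redness and swelling, and the sponsor assigns the intensity. Fever starts at 37.5 °C by oral, axillary or tympanic route and at 38.0 °C rectally. SAP 10.1.3.5 agrees: "The intensity of fever measured by oral, axillary or tympanic route will be scored as defined in the protocol", with a separate scale for rectal readings.

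On collection, the Table 12 note says "Temperature will be recorded in the evening", and protocol 5.6.2.14 says the parents "will record body (axillary/rectal) temperature and any solicited local/general AEs".

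**The concern.** Nothing in these passages makes the daily temperature conditional on a suspicion of fever. A diary can therefore hold both a reading at or above the threshold and a no answer for fever. For that record the SAP offers two results: Grade 0 from the paper-diary rule, and Grade 1 or higher from the temperature scale. A programmer who follows 10.1.2.3.2 to the letter will produce the first. The same applies to redness or swelling answered no with a diameter entered.

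The literal rule works in one direction: it can turn an event into a non-event and never the reverse. Fever is the reaction that the protocol itself reports as more frequent when these two vaccines are given together (sections 1.3.1 and 6.6). Because the study is purely descriptive, the symptom percentages and their exact confidence intervals are the result, and no later test or model would expose the loss.

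**Working it through.** No figure in the plan depends on this rule, so there is nothing to reproduce. The check applies the competing passages to the same records.

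**1. Scope of the rule.** Three consecutive rules in SAP 10.1.2.3.2 deal with not occurred, occurred and unanswered. The second and third are limited to missing recordings. The first refers to all daily measurements. In the later list, the highest observed reading is used only where presence was documented. Followed as written, an infant marked as not having the symptom is never graded from the readings.

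**2. Grading scales.**
- Oral, axillary or tympanic (protocol Table 14): Grade 0 below 37.5 °C; Grade 1 from 37.5 to 38.0; Grade 2 above 38.0 to 39.0; Grade 3 above 39.0.
- Rectal (SAP 10.1.3.5): Grade 0 below 38 °C; Grade 1 from 38.0 to 39.0; Grade 2 above 39.0 to 40.0; Grade 3 above 40.0.

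**3. Constructed records, each with fever answered no.**

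| Route and Day 0 to 3 readings (°C) | Grade from temperature | Grade under the literal rule |
|---|---|---|
| Axillary 36.8, 37.6, 37.0, 36.9 | 1 | 0 |
| Axillary 39.2, 38.1, 37.0, 36.9 | 3 | 0 |
| Rectal 38.2 on all days | 1 | 0 |
| Rectal 37.6 on all days | 0 | 0 (no conflict) |

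The conflict arises for any value at or above its route's threshold, low or high. It does not arise for rectal readings of 37.5 to 37.9 °C, which are not fever on either scale. For redness or swelling, a recorded 5 mm is Grade 1 on the Table 14 scale and Grade 0 under the literal rule.

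**4. Does the numerator table settle it?** The table in SAP 10.1.2.3.2 counts infants with at least one Grade 1, 2 or 3 occurrence, with no condition on the yes/no answer. If the values have already been set to Grade 0, it finds no occurrence. The answer depends on the order of the steps, which the SAP does not state.

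**5. Size per record.** The planned maximum is 340 infants per group. One discordant record changes that symptom's percentage by 1/340 = 0.29 points, slightly more with fewer infants. For scale only, assume 68 of 340 infants truly febrile (20.0%, exact 95% CI 15.9 to 24.7). With no discordant records the rate is unchanged. One gives 67/340 = 19.7%, three give 65/340 = 19.1%, and seven give 61/340 = 17.9% (14.0 to 22.4). Neither the 20% nor the record counts come from the documents.

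**The case against.** The case for leaving the text alone has substance. The rule sits under the heading on missing data, where imputing normally means filling blanks, and the same section says that "missing or non-evaluable measurements will not be replaced". SAP 10.1.3.5 grades fever from temperature without an exception, SAP 5.4.1 reports fever in 0.5 °C steps, and the numerator table ignores the yes/no answer. Site staff collect and verify the diary with the parent at Visit 3 and transcribe it (protocol 5.6.2.14), and inconsistent entries can be queried (protocol 11.1). A discordant record may never reach the analysis.

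Most of this stands. It shows that a blanks-only reading is available and that the literal reading need not be what was intended. It does not show which reading governs. The neighbouring rules say missing when they mean it, the temperature section claims no precedence, and the cleaning steps are general, with no stated check of the answer against the reading.

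A reader might infer more than the documents support:

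- That documented absence on its own overrides the readings. That sentence does not mention readings; the override rests on the Grade 0 rule.
- That every infant with 37.5 °C or more and a no answer is affected. That is wrong for rectal readings below 38.0 °C.
- That the fever rate is biased by several points. No document gives the frequency of such records, or shows that the eCRF can hold a temperature once fever is answered no.
- That the general-symptom and any-symptom percentages fall equally. An infant with another qualifying symptom is still counted there.

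**Conclusion.** The SAP contains an unresolved conflict for records that combine a no answer with a qualifying value for fever, redness or swelling. Under the literal text the value is discarded; under protocol Table 14, and for fever SAP 10.1.3.5, it is graded. If such records remain after data cleaning, the literal rule would understate that symptom's percentage by about 0.3 points per record at 340 infants per group. How many remain is unknown and may be none, so no total effect can be stated. Both groups receive the same vaccines under the same rule, and no hypothesis test depends on it. This is a clarification worth making because the possible error has one direction and the remedy is nearly free. It does not establish that reported rates are wrong.

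**What to change.** In SAP 10.1.2.3.2:

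- Reword the Grade 0 sentence so that it fills only those days with no recorded value.
- Add to that sentence and to the item on documented absence that, for fever, redness and swelling, a recorded value reaching the Table 14 threshold (SAP 10.1.3.5 for rectal readings) is graded from the value, whatever the yes/no answer.
- Query records in which the answer and the value disagree, and list any that remain.

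The cost is about two sentences of text, one programming condition and a short listing. Reported rates may come out slightly higher. If no discordant records exist, no result changes.
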